5.1.2. Prospective cohort

Adult/Adolescent Participant:

- Adult/adolescent study participant from ***any of the prior RSV MAT*** studies who have either received RSV MAT vaccine or control (placebo, Tdap or influenza vaccine).
- Study participant:
 - Who has not reached 2 years+2 months post vaccine/control prior to/at enrollment or
 - Who has reached at least 2 years+2 months post vaccine/control but has an ongoing pregnancy (prior to Day 42 post-delivery) at enrollment. Participants who have reached 2 years post-vaccine/control before enrollment but are pregnant at enrollment will be enrolled and followed until Day 42 post-delivery for the pregnancy ongoing at enrollment.
- Female participants of childbearing potential.
- Provide signed and dated informed consent form.
- Be willing to comply with all study procedures and be available for the duration of the study.

Infant Participant:

- Participant live born as the result of a pregnancy followed in an adolescent/adult participant in this study.
- Participant's parent(s)/LAR(s), in the opinion of the investigator, can and will comply with the requirements of the protocol.
- Signed and dated informed consent form obtained from the participant's parent(s)/LAR(s) prior to performance of any study-specific procedure.

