^a Any study contact may be via telephone, SMS, email, video-telephone/telemedicine or other means, depending on local best practice. If the study site is the participant's primary healthcare facility, contact with study personnel may also be made in the context of a visit for routine or event-driven care.

^b May be combined with another contact where pregnancy is first reported [e.g., combined with Visit 1/Contact 1 (for past/ongoing pregnancies at enrollment), follow-up contact, unscheduled contact.]

^c For participants who are not pregnant at 2 years post vaccine/control, the study conclusion will be completion of the last bi-annual contact, at least 2 months after 2 years post-vaccine/control. If the participant is pregnant at 2 years post vaccine/control **or at study enrollment**, study conclusion will be completion of Day 42 post-delivery. **WONCBP at study enrollment, or recipient of bilateral tube ligation prior to study enrollment will be excluded from the study if she has not conceived a pregnancy post-vaccine/control and does not plan to use any additional measures to attempt to conceive a pregnancy (e.g., sterilization reversal or in vitro fertilization (IVF)).**

^d Any SAEs assessed as related to study participation (e.g., protocol-mandated procedures) or related to a GSK product will be recorded from the time a participant consents to participate in the study.

Table 3 Schedule of Activities for prospective cohort – Infant participant

Type of contact ^a	Delivery ^b	Day 42 Contact ^b	Notes
Timepoints	Day 1	Day 42	
Informed consent	•		Infant informed consent is anticipated at delivery, but may be done at any time up to the delivery contact if allowed at the site (or at Visit 1/Contact 1 for an infant born from a past pregnancy)
Inclusion and exclusion criteria	•		
Demography and lifestyle characteristics	•	•	Demography at birth, and lifestyle at Day 42 post-delivery
Contact information for all HCPs seen by infant from birth through Day 42	○	○	
Safety assessments (from medical record review)			
Record medications/vaccinations	•	•	
Record medically attended AEs until Day 42	•	•	
Infant AESIs from birth until Day 42	•	•	
Infant SAEs from birth until Day 42	•	•	
Record SAEs related to study participation or related to a GSK product ^c	•	•	
MAEs, SAEs and AEs (AESIs) leading to study withdrawal	•	•	
Final Activities			
Study conclusion		•	

• Is used to indicate a study procedure that requires documentation in the individual eCRF.

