5.1. Inclusion criteria

5.1.1. Retrospective cohort

Adult/Adolescent Participant:

- Adult/Adolescent study participant, from *any of the prior RSV MAT* studies who have either received RSV MAT vaccine or control (placebo, Tdap or influenza vaccine).
- Study participant:
 - Who has reached 2 years+2 months post vaccine/control prior to/at enrollment or
 - who has not reached 2 years+2 months post vaccine/control prior to/at enrollment but is a Woman of Nonchildbearing Potential (WONCBP) as defined in Section 10.3.1.2 at study enrollment, or recipient of bilateral tubal ligation prior to study enrollment.
- Study participant with any pregnancy conceived post-vaccination/control, that has reached Day 42 post-delivery prior to/at enrollment.
- Provide signed and dated informed consent form.
- Be willing to comply with all study requirements and be available for the duration of the study.

Infant Participant:

- Participant live born as the result of a pregnancy followed in an adult/adolescent participant in this study.
- Signed and dated informed consent form obtained from the participant's parent(s)/LAR(s) prior to performance of any study-specific procedure.

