5.2. Exclusion criteria

Participants are excluded from the study if any of the following criteria apply:

Adult/adolescent participant otherwise eligible for the prospective cohort:

- Woman of Nonchildbearing Potential (WONCBP) as defined in Section [10.3.1.2](#) at study enrollment, or recipient of bilateral tubal ligation prior to study enrollment, if she has not conceived a pregnancy post-vaccine/control ***and does not plan to use any additional measures to attempt to conceive a pregnancy (e.g., sterilization reversal or IVF).***

Infant participant:

- Child in care.

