10.3.1.2. Woman of Nonchildbearing Potential (WONCBP)

Women in the following categories are considered WONCBP:

Premenarchal: Tanner stage 1 (prepubertal)

Permanently sterile due to one of the following procedures:

- a. Documented hysterectomy
- b. Documented bilateral salpingectomy
- c. Documented bilateral oophorectomy

For permanently sterile individuals due to an alternate medical cause other than the above, (e.g., Mullerian agenesis, androgen insensitivity, gonadal dysgenesis), investigator discretion should be applied to determining study entry. If reproductive status is questionable, additional evaluation should be considered.

Note: Documentation can come from the site personnel's review of the participant's medical records, medical examination, or medical history interview.

Postmenopausal female

A postmenopausal state is defined as no menses for 12 months without an alternative medical cause.

- A high follicle stimulating hormone (FSH) level in the postmenopausal range may be used to confirm a postmenopausal state in women not using hormonal contraception or hormonal replacement therapy (HRT). However, in the absence of 12 months of amenorrhea, confirmation with more than one FSH measurement is required.
- Females on HRT and whose menopausal status is in doubt must discontinue HRT to allow confirmation of postmenopausal status before study enrollment.

Note: the information above is a standard definition of **WONCBP** for interventional studies. No additional medical examination or medical procedures will be conducted to determine if someone is a WONCBP for the purposes of this study.

10.4. Appendix 4: Country-specific requirements.

France specific requirements are included in the additional appendix provided with this protocol.

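### Section 5.1.2 requires childbearing potential while 5.2 keeps some women of nonchildbearing potential, so those pregnant or planning IVF at enrollment fit neither cohort

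*Protocol*

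**What the plan says.** Four parts of the protocol decide who enters which cohort.

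- **Prospective inclusion (5.1.2).** One bullet reads "Female participants of childbearing potential". It has no exception for a woman who has already conceived or plans assisted conception.
- **Exclusion (5.2).** This applies to an "Adult/adolescent participant otherwise eligible for the prospective cohort". A WONCBP or tubal-ligation recipient is excluded "if she has not conceived a pregnancy post-vaccine/control" and "does not plan to use any additional measures to attempt to conceive a pregnancy". Both conditions must hold. Table 2 footnote c repeats the rule: "WONCBP at study enrollment, or recipient of bilateral tube ligation prior to study enrollment will be excluded from the study if she has not conceived", joined to the same second condition.
- **Definitions (10.3.1).** Childbearing potential stops at permanent sterility (10.3.1.1). The list of sterilizing procedures in 10.3.1.2 includes "Documented bilateral salpingectomy", along with hysterectomy and bilateral oophorectomy. Tubal ligation is not on it.
- **Retrospective inclusion (5.1.1).** A WONCBP or tubal-ligation recipient may enter before 2 years+2 months, but every entrant must be a "Study participant with any pregnancy conceived post-vaccination/control, that has reached Day 42 post-delivery prior to/at enrollment".

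Sections 4.1 and 5 assign ongoing pregnancies, up to Day 42 post-delivery, to the prospective cohort and do not mention childbearing potential. The summary of changes for Amendment 2 explains the wording on planned measures: women who plan to conceive during the study are meant to be allowed in. Section 5 forbids waivers of enrollment criteria.

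**The concern.** Section 5.2 is drafted to keep a WONCBP who has conceived or who intends IVF. It operates only on women who already satisfy 5.1.2, however, and no WONCBP can satisfy 5.1.2. For WONCBP the exception is therefore never reached. Amendment 2 lists Table 2, 5.2 and 7.2 as updated for this purpose. The 5.1.2 bullet is not on that list, which suggests a conforming edit was missed.

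At stake is complete capture of pregnancies conceived after vaccine/control, which is the purpose of the study. A site that applies 5.1.2 to the letter must turn away a woman whose pregnancy 4.1 and Section 5 say should be followed, and it cannot grant an exception.

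A second, smaller problem runs the other way. Some tubal-ligation recipients qualify for both cohorts, and follow-up differs between them: it ends at enrollment in the retrospective cohort (4.1, 4.4; SAP 6.2.1) and continues in the prospective one.

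**Working it through.** This is a logic check, so the criteria were applied together to each type of woman. Each row assumes at most one pregnancy since vaccine/control.

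| Woman at enrollment | 5.1.2 | 5.2 | 5.1.1 | Result |
|---|---|---|---|---|
| A. WONCBP, not yet pregnant, before 2 years+2 months, plans IVF | fails | not excluded | fails, no completed pregnancy | neither |
| B. WONCBP, pregnant (e.g. IVF after salpingectomy), any time since vaccine | fails | not excluded | fails, Day 42 not reached | neither |
| C. WONCBP through surgery at delivery, enrolling before Day 42 | fails | not excluded | fails until Day 42 | neither, then retrospective |
| D. WONCBP, pregnancy has reached Day 42 | fails | not excluded | meets | retrospective |
| E. WONCBP, no pregnancy, no plan | fails | excluded | fails | out, as intended |
| F. Tubal ligation, no pregnancy, before 2 years+2 months, plans reversal or IVF | meets | not excluded | fails | prospective |
| G. Tubal ligation, before 2 years+2 months, completed pregnancy | meets | not excluded | meets | both |

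**Rows A to C** are the gap. For row C it closes at Day 42. Rows D and E behave as the plan intends, and row F shows that the 5.2 exception does work for tubal ligation.

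**Row G** is the overlap. Section 4.1 points her to the prospective cohort, because she is within 2 years+2 months. The schema footnote in 1.2 points her to the retrospective cohort, because of the ligation. If she is placed there and later conceives within 2 years of vaccine/control, that pregnancy counts for the any-pregnancy secondary endpoint (Table 5) but is not observed. Her first pregnancy, which is the primary endpoint, is captured either way.

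**Size.** Protocol 9.5 projects about 650 women with a pregnancy. Its inputs give:

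- Prior studies of non-pregnant women: 2540 × 0.10 × 0.60 = 152.4 (plan: about 150).
- Prior studies of pregnant women: 5700 × 0.50 × 0.30 × 0.60 = 513 (plan: about 500).
- Sum: 152.4 + 513 = 665.4, consistent with the plan's rounded 650.

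The documents give no frequency of sterilization or IVF. Taking the affected share as 0.1% to 1% (an assumption):

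- 650 × 0.001 = 0.65 and 650 × 0.01 = 6.5, so about 1 to 7 pregnancies.
- At the 5% rate used in 9.5, these would carry 0.65 × 0.05 = 0.03 to 6.5 × 0.05 = 0.33 expected preterm births, against 650 × 0.05 = 32.5 in the whole study.

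**The case against.** The strongest reply is that the intent can be recovered. Sections 4.1 and 5 place ongoing pregnancies in the prospective cohort without conditions, and the Amendment 2 rationale is explicit. The 5.1.2 bullet also does not cite 10.3.1, whereas 5.1.1 and 5.2 cite 10.3.1.2, so a site might treat a pregnant woman as plainly of childbearing potential. This stands as evidence of intent. It does not remove the conflict: the protocol's glossary makes eligibility a matter of strict adherence to the criteria, 10.3.1.1 has no exception for a sterile woman pregnant by IVF, and waivers are barred.

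A reader might infer more than the documents support:

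- **That all IVF-after-salpingectomy and peripartum-hysterectomy pregnancies are lost.** They are not. Once Day 42 has been reached by enrollment, 5.1.1 admits them. A woman who has a hysterectomy after joining the prospective cohort met the criterion at entry, and withdrawal under 7.2 is then discretionary.
- **That the loss distorts the preterm-birth rate.** Section 9.3.3.2 lists multiple gestation and pregnancy complications as risk factors, but nothing in the documents links them to IVF or to sterilizing surgery, and nothing suggests a difference between arms. At a 5% rate, losing one expected event would require 1 / 0.05 = 20 lost pregnancies.
- **That enrolled populations already differ by site.** This is possible, but the documents do not show it.

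The window is also limited. Vaccination stopped on 28 February 2022 (2.2), and 790 days (Table 4) later is 28 April 2024. Rows A and G cannot arise for enrollments after that date. Row B has no such limit.

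**Conclusion.** The contradiction between 5.1.2 and 5.2 is certain from the text. A WONCBP has no cohort if at enrollment she is pregnant, is within 42 days after delivery, or is before 2 years+2 months and plans IVF. This runs against the stated purpose of Amendment 2. The double eligibility of tubal-ligation recipients with a completed pregnancy is equally certain, but it puts only later pregnancies at risk.

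The effect is probably small: about 1 to 7 of 650 pregnancies if 0.1% to 1% are affected, a range that is assumed and not documented. No bias in the comparison of arms is shown. The point should be corrected because the conflict is plain and the remedy is cheap, not because it threatens the study's conclusions.

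**What to change.** Reconcile Protocol 4.1, Section 5, 5.1.1, 5.1.2, 5.2 and Table 2 footnote c with two edits.

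1. Change the 5.1.2 bullet to: *of childbearing potential, or not excluded under Section 5.2*.
2. Add one cohort-priority rule: *a woman goes to the prospective cohort if she has an ongoing pregnancy (prior to Day 42 post-delivery), or if she is before 2 years+2 months and either can conceive without additional measures or plans such measures; otherwise, a woman with a completed pregnancy conceived post-vaccine/control goes to the retrospective cohort*.

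The rule is needed as well as the bullet. With the bullet alone, a WONCBP before 2 years+2 months with a completed pregnancy would meet both lists, as row G already does. With the rule, rows A and B enter the prospective cohort. Row C does so before Day 42. Row D goes to the prospective cohort if she is before 2 years+2 months and plans to conceive, and otherwise to the retrospective cohort. Row G is placed in the same way as row D.

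The cost is two lines of eligibility text and no new procedures. The downside is that a few extra women will be followed who may not conceive.

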5.2. Exclusion criteria

Participants are excluded from the study if any of the following criteria apply:

Adult/adolescent participant otherwise eligible for the prospective cohort:

- Woman of Nonchildbearing Potential (WONCBP) as defined in Section [10.3.1.2](#) at study enrollment, or recipient of bilateral tubal ligation prior to study enrollment, if she has not conceived a pregnancy post-vaccine/control ***and does not plan to use any additional measures to attempt to conceive a pregnancy (e.g., sterilization reversal or IVF).***

Infant participant:

- Child in care.

5.3. Lifestyle considerations

No lifestyle restrictions are required for this study.

5.4. Screen failures

No screen failures are expected.

5.5. Criteria for temporarily delaying enrollment

Not applicable.

6. STUDY INTERVENTION AND CONCOMITANT THERAPY

Not applicable.

7. PARTICIPANT DISCONTINUATION/WITHDRAWAL

7.1. Discontinuation of study intervention

Not applicable.

7.2. Participant discontinuation/withdrawal from the study

A participant may withdraw from the study at any time at the participant's own request for any reason (or without providing any reason).

A participant may be withdrawn at any time at the discretion of the investigator for compliance reasons. *Investigators may also withdraw participants from the prospective cohort who become a WONCBP as defined in Section 10.3.1.2 or receive bilateral tubal ligation during the prospective follow-up, if they do not plan to use any additional measures to attempt to conceive a pregnancy (e.g., sterilization reversal, or IVF).*

Investigators will attempt to contact participants who do not respond to or complete scheduled follow-up contacts.

All data collected up to and including the date of withdrawal of/last contact with the participant will be included in the study analyses. If the participant withdraws consent for disclosure of future information, the sponsor may retain and continue to use any data collected before such a withdrawal of consent.

The primary reason for participant discontinuation/ withdrawal from the study will be documented in the eCRF based on the list below:

- *Adverse event requiring expedited reporting (AESI and SAE) (prospective cohort only)*
- *Non-serious adverse event (MAE) (prospective cohort only)*

- Death
- Lost to follow-up
- Physician decision
- Protocol deviation
- Site terminated by Sponsor
- Study terminated by Sponsor
- Withdrawal by participant
- ***Migrated/moved from the study area***
- Other (specify).

Participants who are withdrawn from the study because of MAEs/SAEs must be clearly distinguished from participants who are withdrawn for other reasons. Investigator will follow participants who are withdrawn from the study due to a MAE/SAE until the event is resolved (see Section 10.2.3.5).

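### Once a prospective-cohort woman leaves study contacts, no rule secures the birth and infant outcome to Day 42, although medical records could supply it

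*Protocol*

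**What the plan says.** Protocol 2.3 states that nothing is administered in this study. Section 7.2 then makes four relevant provisions.

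- Investigator discretion: "A participant may be withdrawn at any time at the discretion of the investigator for compliance reasons".
- A list of reasons, introduced by "The primary reason for participant discontinuation/ withdrawal from the study will be documented in the eCRF based on the list below". It includes "Adverse event requiring expedited reporting (AESI and SAE) (prospective cohort only" and "Non-serious adverse event (MAE) (prospective cohort only", and also protocol deviation, physician decision and moving out of the study area.
- Use of data: "All data collected up to and including the date of withdrawal of/last contact with the participant will be included in the study analyses". The next sentence covers a participant who withdraws consent to future disclosure; data already held may then be kept.
- Follow-up after withdrawal, for those "withdrawn from the study due to a MAE/SAE until the event is resolved".

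Section 10.2.3.5 requires SAEs and events of special interest to be followed until they are resolved, stabilised or otherwise explained, or the participant is lost. Section 8.4 keeps the investigator responsible for events that led to discontinuation. Section 7.3 dates a loss to follow-up at the last contact.

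On how data are obtained, Table 2 footnote a says "Any study contact may be via telephone, SMS, email, video-telephone/telemedicine or other means, depending on local best practice". Table 2 also has sites note the woman's health-care providers at every contact, and 8.4.5.3 takes outcomes from medical records. Under 5.1.2 an eligible prospective-cohort infant is a "Participant live born as the result of a pregnancy followed in an adolescent/adult participant in this study".

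**The concern.** In a treatment trial, an adverse event can be a reason to stop treatment. Here there is no treatment to stop, and the events named as withdrawal reasons are themselves endpoints or lie on the way to them. Pre-eclampsia and fetal growth restriction are listed pregnancy AESIs (8.4.5.1), and 9.3.3.2 names pre-eclampsia among the risk factors to be explored. Preterm birth is the signal behind the study (2.2).

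If observation stops after such an event and before delivery, the outcome is missing in women whose risk is likely to be raised. Such loss is informative and pulls the incidence of the key safety endpoint down. Women know which product they received (4.5), so the loss may also differ between arms. Section 4.5 discusses selective enrolment but not selective attrition. Moving away or missing contacts need not end data collection when contacts can be remote and the outcome is in a medical record.

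**Working it through.** **1. What the endpoints need.** Section 3 and 8.4.5.1 require pregnancy outcome, gestational age at birth, birth weight and infant status up to Day 42 post-delivery.

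**2. What the plan secures after each kind of departure.**

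| Reason for leaving | Follow-up the text requires | Reaches delivery and Day 42? |
|---|---|---|
| MAE or SAE | Until that event resolves (7.2) | Only if the event lasts that long |
| AESI | Until resolved, stabilised or explained (10.2.3.5) | Only if the event lasts that long |
| Compliance, protocol deviation or moving, no open event | None stated | No |
| Loss of contact | None; dated at last contact (7.3) | No |

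No section provides for collecting the birth or infant outcome after withdrawal.

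**3. A case under the text.** A prospective-cohort woman has fetal growth restriction recorded as an AESI, then leaves contacts. The event is judged stabilised and she later delivers preterm. The AESI is in the data. The preterm birth, birth weight and infant status need not be. Whether her infant still comes from a followed pregnancy under 5.1.2 is unclear.

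**4. What the analysis does.** SAP 4.1.1 does not impute missing values and leaves them out. SAP 4.2.2 counts only pregnancies and infants with medical-record data. SAP 6.1.1 tabulates withdrawals and reasons by arm, which shows the loss but recovers no outcome. The sensitivity-analysis section (4.2.3) is blacked out and cannot be judged.

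**5. The plan's own figures reproduce.** Expected women with a pregnancy: 2540 × 0.10 × 0.60 + 5700 × 0.50 × 0.30 × 0.60 = 152.4 + 513.0 = 665.4, against about 650 stated. Probability of at least one event with n = 100 at 5%: 1 − 0.95^100 = 99.4%, as stated. Exact 95% CI for 15/300: 2.8% to 8.1%, as stated. None of these allows for outcomes lost after withdrawal, and no withdrawal rate is given.

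**6. Direction and sensitivity; the loss fractions are assumed.** Let p be the true preterm rate, f the share of preterm births lost and g the share of other pregnancies lost. Then

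observed rate = p(1 − f) / [p(1 − f) + (1 − p)(1 − g)].

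Take p = 5% (the rate used in 9.5) and g = 2% (assumed):

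- f = 10%: 0.0450 / (0.0450 + 0.9310) = 4.61%
- f = 20%: 0.0400 / (0.0400 + 0.9310) = 4.12%
- f = 30%: 0.0350 / (0.0350 + 0.9310) = 3.62%

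For the relative risk, assume true rates of 7% and 5% (1.40) and the same g:

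- f equal in both arms, at 10%, 20% or 30%: 1.40 to 1.41
- f = 20% in the 7% arm, 10% in the other: 5.79 / 4.61 = 1.26
- f = 30% and 10%: 5.10 / 4.61 = 1.11
- f = 10% and 30%: 6.47 / 3.62 = 1.78

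These apply only to pregnancies ongoing at enrolment or conceived later. Pregnancies already past Day 42 at enrolment cannot be lost this way, so the pooled effect is smaller, by a mix of cohorts that the documents do not give.

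**The case against.** The strongest reply is that the list only codes reasons. It also contains death and loss to follow-up, which are statuses and not decisions. A reader might infer that 7.2 directs withdrawal when an endpoint event occurs. It does not. The only investigator grounds in its body are compliance and becoming unable to conceive. Still, the schedules of activities carry a row for events leading to withdrawal at every scheduled maternal contact and both infant contacts, so the plan expects such withdrawals.

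A reader might also infer that 7.2 bars data after withdrawal, and so contradicts its own follow-up duty. The text does not support that. It says data up to withdrawal are included and is silent on later data. The separate sentence on consent to future disclosure suggests collection might otherwise continue, and the Full Analysis Set does not exclude withdrawn women. The fault is silence, not contradiction.

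Preterm labour followed by withdrawal is a tempting example, but Table 22 requires a preterm delivery at every level of that definition. The mechanism holds for antenatal events such as pre-eclampsia or fetal growth restriction. Even there, an event that lasts until birth carries follow-up to birth under the resolution wording, though not necessarily where stabilisation is enough.

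Finally, a pregnancy followed up to withdrawal is arguably still a followed pregnancy, infant consent can be taken before delivery where the site allows, and the by-arm withdrawal tables would show an imbalance. These points narrow the gap. They do not supply the missing birth outcome.

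**Conclusion.** The point holds as a cheap improvement. Following the plan as written can leave a prospective-cohort pregnancy without a birth or infant outcome after the woman stops contacts, whether because of an antenatal event, compliance, moving or loss of contact. The expected direction is a lower observed incidence, given that loss is more likely in pregnancies at raised risk. A distorted arm comparison requires the loss to differ by arm, which is possible because arm is known but is not shown to happen.

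The size cannot be derived: the documents give no withdrawal rate, no share of pregnancies with a predisposing event and no split between cohorts. The figures under the assumed loss show sensitivity only. A reader might be tempted to apply a percentage bias to all 650 expected women. That is unsupported, because the adverse-event reasons are confined to the prospective cohort and retrospective pregnancies have already reached Day 42 at enrolment (5.1.1).

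**What to change.** In Protocol 7.2, with matching text in 7.3:

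1. State that the end of study contacts, for an adverse event, non-compliance, protocol deviation, moving or loss of contact, does not end record-based collection of pregnancy outcome, gestational age at birth and infant status through Day 42. Use the provider details sites already hold. The exception is a participant who withdraws consent to disclosure of future information, a category 7.2 already has.
2. State that these data enter the analyses.
3. In 5.1.2, state that the infant of such a pregnancy remains eligible, subject to infant consent.
4. In SAP 6.1.1, add the number of pregnancies with unknown outcome by arm.

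Keep the reason codes as they are. Limiting them to a participant's own request would remove an honest record of withdrawals started by the investigator.

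Cost: the consent form must cover access to records after contacts stop, and each affected pregnancy needs one record review. No new visits or data sources are needed.
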